## **10 SAFETY ANALYSES**

### **10.1 Extent of exposure**

#### **10.1.1 Part A**

Exposure to study medication in Part A will be evaluated by summarizing the total number of CZP injections, the total amount of CZP received in mg, the total drug exposure duration in days, the patient time at risk and the total patient years at risk. Summaries will be based on the SS and presented by axSpA subpopulation and overall.

Duration of exposure to study medication in Part A will be calculated (in days) as:

- The date of the last Part A injection – date of first Part A injection + 14 days.

If the first study medication administration in Part B, final contact date or death occurs prior to the completion of the 14-day period, exposure to study medication in Part A will be censored at the earliest of these events.

Patient time at risk in Part A will be calculated (in days) as:

- The date of the last injection in Part A – date of first injection in Part A + 70 days

If the first study medication administration in Part B, final contact date or death occurs prior to the completion of the 70-day period, patient time at risk in Part A will be censored at the earliest of these events.

Total patient years at risk will be calculated as the sum of all the relevant patient time at risk (in days) divided by 365.25.

## **10.1.2        Part B**

### **10.1.2.1      All subjects in SSB – Prior to Flare**

Exposure to study medication in Part B will be evaluated by summarizing the total number of CZP or PBO injections, the total number of CZP injections, the total amount of CZP received in mg, the total drug exposure duration in days, the patient time at risk and the total patient years at risk. Summaries will be based on the SSB and presented by treatment group.

Duration of exposure to study medication in Part B will be calculated (in days) for subjects who do not experience a flare as:

- The date of the last CZP 200mg or PBO Part B injection – date of Week 48 injection + 14 days for subjects in the 200mg CZP Q2W and PBO groups [1]
- The date of the last CZP 200mg Part B injection – date of Week 48 injection + 28 days for subjects in the 200mg CZP Q4W group [2]

Duration of exposure to study medication in Part B will be calculated (in days) for subjects who do experience a flare as:

- The date of the last CZP 200mg or PBO Part B injection prior to start of escape full-dose CZP – date of Week 48 injection + 14 days for subjects in the 200mg CZP Q2W and PBO groups [3]
- The date of the last CZP 200mg Part B injection prior to start of escape full-dose CZP – date of Week 48 injection + 28 days for subjects in the 200mg CZP Q4W group [4]

If the final contact date or death occurs prior to the completion of the 14-day period for [1] or prior to the completion of the 28-day period for [2], exposure to study medication in Part B will be censored at the earliest of these events. If the start of escape full-dose CZP occurs prior to the completion of the 14-day period for [3] or prior to the completion of the 28-day period for [4], exposure to study medication in Part B will be censored at the date of this event.

Patient time at risk in Part B will be calculated (in days) for subjects who do not experience a flare as:

- The date of the last CZP 200mg or PBO Part B injection – date of Week 48 injection + 70 days for subjects in the 200mg CZP Q2W and PBO groups [1]
- The date of the last CZP 200mg Part B injection – date of Week 48 injection + 70 days for subjects in the 200mg CZP Q4W group [2]

Patient time at risk in Part B will be calculated (in days) for subjects who do experience a flare as:

- The date of the last CZP 200mg or PBO Part B injection prior to start of escape full-dose CZP – date of Week 48 injection + 70 days for subjects in the 200mg CZP Q2W and PBO groups [3]
- The date of the last CZP 200mg Part B injection prior to start of escape full-dose CZP – date of Week 48 injection + 70 days for subjects in the 200mg CZP Q4W group [3]

If the final contact date or death occurs prior to the completion of the 70-day period for [1] or [2], patient time at risk in Part B will be censored at the earliest of these events. If the start of escape full-dose CZP occurs prior to the completion of the 70-day period for [3] and [4], patient time at risk in Part B will be censored at the date of this event.

Total patient years at risk will be calculated as the sum of all the relevant patient time at risk (in days) divided by 365.25.

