#### **Period 4 (Safety Follow Up Period): 10 weeks after the last dose of study medication**

All subjects, including those withdrawn from study treatment, will have a Safety Follow Up (SFU) Visit 10 weeks after their last dose of study medication. Subjects in UK will be followed up additionally for 12 weeks after the SFU Visit, by phone call for occurrence of any clinically significant infections, including tuberculosis.

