#### **2.3.4 Study duration per subject**

For each subject, there is a planned duration of up to 109 weeks, as follows:

- Up to 5 weeks of Screening Period
- 48 weeks in the Open-Label Period
- 48 weeks in the Double-Blind Period

- An SFU Visit 10 weeks after last dose administration (Period 4).

Of note, the last dosing in the Double-Blind Period occurs at Week 94 so that the SFU of 10 weeks already includes 2 weeks from the Double-Blind Period hence leading to a duration of 109 weeks.

Subjects in UK will be contacted by a telephone call 22 weeks after the last dose of their study medication hence leading to a duration of 121 weeks.

For subjects who experience a flare during the Double-Blind Period, the study duration might be prolonged.

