### **3.4 Definition of Baseline values**

The study baseline value for a subject noted “Part A Baseline” will be defined as the latest measurement for that subject up to and including the day of administration of first study medication in Part A, unless otherwise stated. If a Part A Baseline measurement is missing or not collected, and a Screening value is available, the Screening value will be utilized as Part A Baseline instead. If no measurement is available prior to receiving study medication in Part A, the Part A Baseline value is treated as missing.

For subjects randomized into Part B, a “Part B Baseline” will be defined as the latest measurement for that subject up to and including the day of randomization, unless otherwise stated. If a Part B Baseline measurement is missing or not collected, and a post-Baseline Part A value is available, the post-Baseline Part A value will be utilized as Part B Baseline instead. If no post-Baseline Part A measurement is available prior to randomization, the Part B Baseline value is treated as missing.

For subjects experiencing a flare in Part B, a “Flare Baseline” will be defined as the latest measurement for that subject up to and including the day of administration of first escape treatment in Part B, unless otherwise stated. If a Flare Baseline measurement is missing or not collected, and a post-Baseline Part B value is available, the post-Baseline Part B value will be utilized as Flare Baseline instead. If no post-Baseline Part B measurement is available prior to receiving study medication in Escape Part, the Flare Baseline value is treated as missing. If a subject does not receive study medication in Escape Part, the last available post-Baseline Part B measurement will be used as Flare Baseline.

For each baseline definition, if there is evidence that measurements taken on the same day as administration of first study medication (in Part A/Part B) or first escape treatment (for subjects experiencing a flare in Part B) were actually taken after this administration, then only values strictly prior to that date (including screening assessment visits if appropriate) will be used for that subject. When the date of first dose is derived, it should be based on the first injection of study treatment, regardless of whether it is an active treatment.

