### Treatment-Emergent AEs (TEAEs)

Treatment emergent AEs (TEAEs) will be defined and summarized in four different ways:

[1] TEAEs in Part A: will be defined as all AEs starting on or after the date of first study medication in Part A and up to 70 days after the last dose of study medication in Part A and before the date of the first study medication in Part B if any.

[2] TEAEs in Part B prior to flare: will be defined as all AEs starting on or after the date of first study medication in Part B and up to 70 days after the last dose of study medication in Part B. AEs occurring more than 70 days after the last dose in Part B will not be considered treatment emergent, regardless of whether this occurs during the SFU period, or after a treatment gap of more than 70 days. AEs which emerge post-flare will be excluded from any summary tables of TEAEs in Part B prior to flare.

[3] TEAEs in Part B in subjects experiencing a flare: Pre-flare TEAEs in Part B will be defined as any TEAEs in Part B with an onset date before the start date of escape therapy. Post-flare TEAEs in Part B will be defined as any TEAEs in Part B with an onset date on or after the start date of escape therapy.

[4] TEAEs in Part B under CZP full-dose therapy: These will be defined for subjects in the FDS who ever received a dose of CZP 200mg Q2W during Part B as double-blind or as escape treatment.

TEAEs in Part B under CZP full-dose therapy will be defined as follows:

- In subjects randomized into Part B to the PBO or CZP 200mg Q4W arm who do experience a flare and do escape to CZP full-dose therapy, TEAEs under CZP full-dose therapy will include all post-flare TEAEs in Part B
- In subjects randomized into Part B to CZP 200mg Q2W arm, TEAEs under CZP full-dose therapy will include all TEAEs in Part B

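### Half-dose (Q4W) time at risk in Part B runs from the last active injection, while adverse events count from the last injection of any kind, so the denominator can be up to 14 days short

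*SAP*

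**What the plan says.** Section 10.1.2.1 (prior to flare) sets Part B patient time at risk by arm. For the full-dose (Q2W) and placebo arms without flare it is "The date of the last CZP 200mg or PBO Part B injection – date of Week 48 injection + 70 days for subjects" in those groups. For the half-dose arm it is "The date of the last CZP 200mg Part B injection – date of Week 48 injection + 70 days for subjects in the" Q4W group. The bullets for flared subjects keep the same split, with the last injection taken before escape.

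Section 10.2 has one rule for Part B treatment-emergent events in all arms: they count from the first Part B study medication "up to 70 days after the last dose of study medication in Part B". The same section uses patient-years at risk as the denominator of both EAIR and EAER.

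The SAP treats placebo injections as study medication. The opening of section 10.1.2.1 reads "Exposure to study medication in Part B will be evaluated by summarizing the total number of CZP or PBO injections". Section 3.4, speaking only of the first dose, counts an injection "regardless of whether it is an active treatment". Section 2.3.4 states that "the last dosing in the Double-Blind Period occurs at Week 94", and the safety follow-up visit takes place "10 weeks after their last dose of study medication".

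**The concern.** EAIR and EAER are the exposure-adjusted summaries through which readers will compare full dose, half dose and withdrawal. In two arms the event window and the time at risk end on the same day. In the Q4W arm they need not: an event late in follow-up can enter the numerator after that subject's person-time has stopped. In the EAIR, such a subject's time to first event can exceed the whole of the defined time at risk. The error affects one arm only and always raises the Q4W rate.

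A principle of counting only active drug does not explain the split, because the placebo arm's time at risk is built entirely from placebo injections.

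**Working it through.** **Inputs from the SAP**
- Time-at-risk and exposure rules: section 10.1.2.1.
- Event window: section 10.2.
- Last double-blind dosing at Week 94: section 2.3.4.
- 70 subjects per arm, 75% of Q4W assumed free of flare: section 2.4.

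**Reproducing the plan's own figure.** Duration per subject is 5 + 48 + 48 + 10 − 2 = 109 weeks, as section 2.3.4 states. Last dosing at Week 94 therefore puts the end of the 70-day follow-up at Week 104. Censoring at final contact does not shorten this for a subject who attends the follow-up visit.

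**Which week carries the last active Q4W dose?** The SAP does not say. Alternating placebo is inferred from three things: the double-blind design, the contrast between the two anchors, and the two-week compliance steps to Week 94 in section 12.2, which make no exception by arm. The exposure rule for Q4W, "The date of the last CZP 200mg Part B injection – date of Week 48 injection + 28 days for subjects in the" Q4W group, gives a further check:
- Last active at Week 92: (92 − 48) × 7 + 28 = 308 + 28 = 336 days. The other arms give (94 − 48) × 7 + 14 = 322 + 14 = 336 days, and 48 weeks is also 336 days.
- Last active at Week 94: 322 + 28 = 350 days, longer than the 48-week period.

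Week 92 is the better fit, and it is used below as an assumption.

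**Completer without flare**

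| Arm | Event window (days) | Time at risk (days) | Ratio |
|---|---|---|---|
| Q2W, placebo | 322 + 70 = 392 | 322 + 70 = 392 | 1.000 |
| Q4W, last active at Week 92 | 322 + 70 = 392 | 308 + 70 = 378 | 392/378 = 1.037 |
| Q4W, last active at Week 94 | 392 | 392 | 1.000 |

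Under a constant event rate the EAER of a Week 92 completer is 3.7% too high. For example, a true 200 per 100 patient-years becomes 200 × 392/378 = 207.

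**EAER for the whole arm.** Let s be the share without flare. The rest are assumed to escape on average T days after Week 48, where both clocks stop. The ratio is [392s + (1 − s)T] / [378s + (1 − s)T].
- s = 0.75, T = 84: 315/304.5 = 1.034. With T = 252: 357/346.5 = 1.030.
- s = 0.50, T = 252: 322/315 = 1.022.
- s = 0.90, T = 84: 361.2/348.6 = 1.036.

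Person-time lost at 75% without flare is 0.75 × 70 × 14/365.25 = 2.0 patient-years. The most possible, with all 70 free of flare, is 70 × 14/365.25 = 2.7.

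**EAIR, completer without flare.** Subjects with the event contribute time to first occurrence, so only event-free subjects lose the 14 days. Take a constant first-event rate λ per patient-year, t = 392/365.25 and u = 378/365.25, with time to first event counted up to t. The calculated rate is (1 − e^(−λt)) / [(1 − e^(−λt))/λ − e^(−λt)(t − u)]. Its excess over λ is 3.6% at λ = 0.05, 2.8% at λ = 0.5 and 1.5% at λ = 1.5.

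**Withdrawal without escape.** If the last injection was active, no days are lost. If it was placebo, 14 days are lost, whichever calendar applies.

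**The case against.** Three arguments stand on the other side.

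- **The calendar is not stated.** If the last active Q4W dose is at Week 94, completers show no gap, and the 3.7% and the 2.0 patient-years fall away. This stands as a condition on the size. It does not remove the mismatch for subjects who withdraw after a placebo injection.
- **The event window could be read differently.** Section 10.2 does not define the last dose of study medication for Q4W, and section 10.1.2.1 itself uses the last active injection when it measures Q4W exposure. A programmer could carry that anchor into the event window, and the two clocks would then agree within the arm. But the same section counts CZP and placebo injections together as study medication, and section 10.2 makes no exception for Q4W. That reading would need its own change to the stated event rule, so the text needs repair either way.
- **The consequence is small.** Escapers are unaffected, because both clocks stop at the start of escape. The numbers and percentages of subjects with events are unchanged. No between-arm test of EAIR or EAER is planned, and EAER has no confidence interval. With 10 affected subjects an exact 95% interval runs from about 4.8 to 18.4 events, roughly −52% to +84%, which dwarfs a shift of 2-4%. This stands in full and sets the severity.

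A reader might infer that all half-dose safety rates are overstated by 3.7%, or that the half dose will be made to look materially less safe than the other arms. The SAP supports neither. The 3.7% belongs to the EAER of one kind of subject under an inferred calendar, and nothing suggests that a safety conclusion would change.

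**Conclusion.** The mismatch is real as written. Q4W time at risk and the Q4W event window have different end points whenever the last Part B injection was placebo and the subject did not escape, and nothing in the SAP reconciles them. The gap is at most 14 days per subject and occurs only in the half-dose arm.

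Its size depends on the calendar. With the last active dose at Week 92, the likelier reading, EAER is about 2-4% too high for the arm, and EAIR is about 1.5-3.6% too high for completers, depending on the event rate. The arm-level range also assumes a constant event rate, 50-90% of the arm free of flare, and escape on average 84 to 252 days after Week 48. With the last active dose at Week 94, only withdrawals after a placebo injection contribute. Severity: minor.

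**What to change.** In SAP section 10.1.2.1, define Q4W patient time at risk from the last CZP 200mg or placebo Part B injection + 70 days, as for the other two arms. Do this in both the no-flare and the flare bullets, taking the last injection before escape in the latter. The denominator then matches the event window in section 10.2; for a Week 92 completer it returns to 392 days.

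Leave the +28-day rule for exposure duration as it is: it measures something else and gives 336 days in every arm under the Week 92 calendar.

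In the same edit, relabel the flared Q4W time-at-risk bullet from [3] to [4], since the censoring sentence below it refers to [4] and no bullet in that list carries that label.

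Cost: two lines of wording, one label and one derivation. No new data are needed.

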### **3.2.22 Flare**

A subject is considered to have experienced a flare if a subject has an ASDAS  $\geq 2.1$  at 2 consecutive visits or an ASDAS  $>3.5$  at any visit during Part B up until Week 96.

If a subject has an intermittent missing ASDAS score (ie, a missing value at 1 visit but non-missing values at the previous and subsequent visit), then the missing value will be ignored and the occurrence of a flare will be based on the 2 available values.

If the ASDAS score is missing at 2 or more consecutive visits, then the subject will be considered to have experienced a flare (even if ASDAS scores are available after the missed visits).

There is also the possibility to report one unscheduled ASDAS between two scheduled ASDAS assessments. The same rules as for the scheduled ASDAS apply for the unscheduled ASDAS.

The unscheduled ASDAS will be taken into account for flare calculation for two consecutive visits if there are more than 13 calendar days between two consecutive ASDAS calculated dates.

If the ASDAS score is missing at 2 scheduled visits and unscheduled ASDAS entry present in between and not larger than 3.5, then the subject will not be considered to have experienced a flare.

Occurrence of a flare will be based solely on the observed ASDAS values and will not take into account any imputation of ASDAS. Occurrence of a flare will be determined based on the actual

data entered into the eCRF for the individual ASDAS components, not based on data from the interactive voice or web response system (IXRS).

If a subject prematurely withdraws from Part B at any point for any reason, then the subject will be considered to have experienced a flare.

If a subject was incorrectly identified as flared at any point in Part B due to late data entry in IXRS and went to escape Part B, then the subject will be considered to have experienced a flare.

Sensitivity analyses will be conducted using different approaches for definition of flare. These approaches are described hereafter.

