## **5 STUDY POPULATION CHARACTERISTICS**

### **5.1 Subject disposition**

The number and percentage of subjects who entered the study, completed Part A, discontinued from Part A with reasons for discontinuation, were randomized into Part B, completed Part B (without flare, after flare) and discontinued Part B as well as started Escape Part, completed Escape Part and discontinued Escape Part with reasons for discontinuation will be presented.

Subjects who completed Week 48 without SFU are considered as completed Part A. Subjects completed Week 96 in Part B or in Escape Part without SFU visit are considered as completed Part B or completed Escape Part, respectively.

Subjects are considered to have started Escape Part, if they experienced a flare and have been moved to escape treatment via IXRS system (even if they do not receive any escape treatment).

This summary will be based on the ES and will present subjects overall and broken out by axSpA subpopulation.

Discontinuations due to AEs will also be presented. This summary will be based on the ES and will present subjects overall and broken out by axSpA subpopulation.

The disposition of subjects screened by geographical region and overall, including the number of subjects in each analysis set will be summarized. This summary will be based on the ES and will present subjects overall (ie not broken out by axSpA subpopulation).

A summary table of reasons for screen failures will be provided.

The following listings will be produced based on the ES:

- A listing of subject analysis sets
- A listing of subjects who did not meet study eligibility criteria
- A listing of subject disposition

The following listings will be produced based on the OLS:

- A listing of study discontinuation
- A listing of visit dates
- A listing of important protocol deviations (including any reasons for exclusion from the PPS)

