#### **10.1.2.3 Full-dose CZP in Part B**

Exposure to full-dose CZP in Part B will be evaluated by summarizing the total number of CZP injections, the total amount of CZP received in mg, the total drug exposure duration in days, the patient time at risk and the total patient years at risk. Summaries will be based on the FDS. These summaries will be produced presenting a single column “CZP full-dose in Part B (CZP 200mg Q2W)”.

Duration of exposure to full-dose CZP in Part B as double-blind or as escape treatment will be calculated (in days) as:

- The date of the last escape full-dose CZP injection – date of the first escape full-dose CZP injection + 14 days for subjects in the 200mg CZP Q4W and PBO groups who escape to full-dose CZP therapy
- The date of the last escape full-dose CZP injection – date of Week 48 injection + 14 days for subjects in the 200mg CZP Q2W group experiencing a flare
- The date of the last Part B injection – date of Week 48 injection + 14 days for subjects in the 200mg CZP Q2W group who did not flare

If final contact or death occurs prior to the completion of the 14-day period, the exposure duration will be censored at the date of the earliest event.

Patient time at risk in Part B under full-dose CZP therapy will be calculated (in days) as:

- The date of the last escape full-dose CZP injection – date of the first escape full-dose CZP injection + 70 days for subjects in the 200mg CZP Q4W and PBO groups who escape to full-dose CZP therapy
- The date of the last escape full-dose CZP injection – date of Week 48 injection + 70 days for subjects in the 200mg CZP Q2W group experiencing a flare
- The date of the last Part B injection – date of Week 48 injection + 70 days for subjects in the 200mg CZP Q2W group who did not flare

If final contact or death occurs prior to the completion of the 70-day period, the patient time at risk will be censored at the date of the earliest event.

Total patient years at risk will be calculated as the sum of all the relevant patient time at risk (in days) divided by 365.25.

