- The date of the last Part A full-dose CZP injection – date of first Part A full-dose CZP injection + 70 days for subjects not randomized into Part B. Patient time at risk will be censored at the date of earliest of the following events if any of these events occur prior to the completion of the 70-day period: final contact or death.
- The date of the last Part A full-dose CZP injection – date of first Part A full-dose CZP injection + 70 days for subjects randomized into Part B to the PBO or CZP 200mg Q4W arms who do not experience a flare and do not escape to CZP full-dose therapy. Patient time at risk will be censored at the date of earliest of the following events if any of these events occur prior to the completion of the 70-day period (first study medication administration in Part B, final contact or death).
- The sum of (date of the last Part A full-dose CZP injection – date of first Part A full-dose CZP injection + 70 days) [1] and (date of the last escape full-dose CZP injection – date of first escape full-dose CZP injection + 70 days) [2] for subjects randomized into Part B to the PBO or CZP 200mg Q4W arms who do experience a flare and do escape to CZP full-dose therapy. If first study medication administration in Part B occurs prior to the completion of the 70-day period for [1], [1] will be censored at the date of this event. If final contact or death occurs prior to the completion of the 70-day period for [2], [2] will be censored at the date of the earliest event.
- The date of the last Part B injection – date of first Part A full-dose CZP injection + 70 days for subjects randomized into Part B to CZP 200mg Q2W arm. If final contact or death occurs prior to the completion of the 70-day period, the patient time at risk will be censored at the date of the earliest event.

Total patient years at risk will be calculated as the sum of all the relevant patient time at risk (in days) divided by 365.25.

Exposure data will be listed.

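### Section 10.1 branches safety exposure on an undefined flare status, so flared subjects with no escape dose get uncensored, uncomputable or unassigned time at risk

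*SAP*

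**What the plan says.** **Who has flared.** Section 3.2.22, a general study-level definition, states: "If a subject prematurely withdraws from Part B at any point for any reason, then the subject will be considered to have experienced a flare". It adds a second route that needs no escape: "If the ASDAS score is missing at 2 or more consecutive visits, then the subject will be considered to have experienced a flare". Section 5.1 counts a subject as having started the Escape Part once "moved to escape treatment via IXRS system (even if they do not receive any escape treatment". Flare and receipt of an escape dose are therefore different things.

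**Section 10.1.2.1 (Part B before flare).** Subjects without a flare are branches [1] and [2]; subjects with a flare are [3] and [4]. The flared formula for Q2W and placebo, in days, is "The date of the last CZP 200mg or PBO Part B injection prior to start of escape full-dose CZP – date of Week 48 injection + 70". The non-flared branches are censored at final contact or death: "If the final contact date or death occurs prior to the completion of the 70-day period for [1] or [2". The flared branches have a different trigger only: "If the start of escape full-dose CZP occurs prior to the completion of the 70-day period for [3] and [4". The exposure-duration rule in the same section has the same split, with windows of 14 days (Q2W, placebo) and 28 days (Q4W). The time-at-risk bullet for flared Q4W subjects is labelled [3], although the censoring sentence refers to [4].

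**Section 10.1.2.3 (full dose in Part B).** Time at risk runs from the Week 48 injection to the last escape injection, "70 days for subjects in the 200mg CZP Q2W group experiencing a flare". The only other Q2W bullet is for subjects who did not flare. Final-contact and death censoring is present here.

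**Section 10.1.3 (full dose in Parts A and B).** One placebo/Q4W rule covers subjects "who do not experience a flare and do not escape to CZP full-dose therapy"; the other covers those who both flare and escape. The closing TEAE bullets of Section 10.2, on events while on the Q2W dose, use the same two categories.

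**The concern.** A subject who withdraws, dies or is lost in Part B without an escape dose has flared under Section 3.2.22 but has no escape date. The time-at-risk rules use flare as if it meant that escape had started. For this subject one rule gives too much time, one needs a date that does not exist, and one has no matching category.

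These times are the denominators of the exposure-adjusted incidence and event rates in Section 10.2. The affected subjects include those who stopped for an adverse event or died, so they matter for safety, and a programmer would have to improvise the rule for them.

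**Working it through.** There is no plan figure to reproduce; the check applies the rules as written. Day 0 is the Week 48 injection.

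**1. Section 10.1.2.1.** Assume the last injection on day 84, death or last contact on day 94, and no escape.

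- As written for a flared subject: 84 + 70 = 154 days.
- With final-contact/death censoring: 94 days. Excess: 60 days.
- In general, excess = 70 minus the days from last injection to final contact or death. Gaps of 0, 10, 28, 42 and 70 days give 70, 60, 42, 28 and 0 days.
- Exposure duration for the same subject: 84 + 14 = 98 days (Q2W, placebo) or 84 + 28 = 112 days (Q4W), against 94.

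Scale: a completer has 46 × 7 + 70 = 392 days, so 70 completers give 70 × 392 / 365.25 = 75.1 patient-years (PY). Assuming 1 to 10 affected subjects with 30 to 70 excess days each, the excess is 1 × 30 / 365.25 = 0.08 PY to 10 × 70 / 365.25 = 1.92 PY, or 0.1% to 2.6% of the arm's time.

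**2. Section 10.1.2.3.** A flared Q2W subject without escape has no end date. Section 10.2 (TEAE definition [4]) nevertheless counts all Part B TEAEs of the Q2W arm. Assume n Q2W subjects (5%, 10% or 15% of 70) withdraw without escape halfway through Part B, last injection 22 weeks after Week 48: 22 × 7 + 70 = 224 days = 0.613 PY each. The table is one pooled column, so escapers from placebo and Q4W belong in the denominator. With the non-flare rates of Section 2.4 (75% and 45%), flares in those arms number 17.5 + 38.5 = 56. Removing 2n withdrawals leaves 56 − 2n escapers, each assumed to contribute 0.613 PY.

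| Assumed share | 5% | 10% | 15% |
|---|---|---|---|
| n (Q2W) | 3.5 | 7 | 10.5 |
| Missing time, n × 0.613 | 2.1 PY | 4.3 PY | 6.4 PY |
| Full Q2W time, (70 − n) × 392/365.25 + n × 0.613 | 73.5 | 71.9 | 70.3 |
| Escape time, (56 − 2n) × 0.613 | 30.1 | 25.8 | 21.5 |
| Missing share of pooled time | 2.1% | 4.4% | 7.0% |

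With the events kept in, the pooled event rate is overstated by a factor of 1/(1 − share).

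**3. Section 10.1.3.** Each placebo/Q4W subject who flared without escape leaves 48 × 7 = 336 days = 0.92 PY of Part A time unassigned. For 7, 14 and 21 subjects of 140 this is 6.4, 12.9 and 19.3 PY.

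The pooled total depends on the 750 − 210 = 540 non-randomized subjects. Assume they contribute 100% or 50% of 392 days each.

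- High (100%, 5% share): 579.6 non-randomized + 137.9 Q2W + 128.8 placebo/Q4W Part A + 30.1 escape ≈ 876 PY.
- Low (50%, 15% share): 289.8 + 134.7 + 128.8 + 21.5 ≈ 575 PY.

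Q2W completers count 94 × 7 + 70 = 728 days and mid-period withdrawals 70 × 7 + 70 = 560 days. The unassigned share runs from 6.4/876 = 0.7% to 19.3/575 = 3.4%. The closing bullets of Section 10.2 also give no rule for these subjects' events, so numerator and denominator are both unassigned.

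**The case against.** The best defence is that flare in Section 10.1 is operational. Section 4.2 ties the rule that withdrawal equals flare to the primary variable, as an imputation for analysis. Table 3.3 censors withdrawals for other reasons under two of its three approaches. Section 3.6.9 bases the Flared Set on IXRS and entry to the Escape Part, and Section 10.2 separates pre- from post-flare events at the start of escape therapy. On that reading a withdrawn subject who never entered escape is non-flared, and all three gaps close for that subject.

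This narrows the problem but does not remove it. Section 10.1 names no definition, and Section 3.2.22 takes flare from eCRF data rather than IXRS. Sections 3.1, 10.3 and 10.4.1 state flaring and starting escape therapy as two conditions, which suggests that the SAP keeps them apart. Even under IXRS, a subject moved to escape but never dosed still falls into the gaps.

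Other points stand. Section 2.3.2 requires a visit 10 weeks after the last dose, also for withdrawn subjects, so the 70 days in Section 10.1.2.1 are right unless the subject dies or is lost earlier.

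A reader might infer that full-dose time of withdrawn Q2W subjects is missing throughout. It is not: Section 10.1.3 times all Q2W subjects to the last Part B injection regardless of flare. A reader might also infer that the Part A data disappear, but Section 10.1.1 and TEAE definition [1] still report them. Nor do all tables err in a known direction: in Section 10.1.3 time and events drop out together, so no direction follows.

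**Conclusion.** The point holds as a gap in the rules, and it should be fixed. For flared subjects without an escape dose:

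- Section 10.1.2.1 overstates exposure and time at risk when death or last contact falls inside the 14-, 28- or 70-day window. Time at risk is overstated by at most 70 days per subject, which lowers the rate.
- Section 10.1.2.3 gives Q2W subjects no time while counting their events, which raises the pooled full-dose rate.
- Section 10.1.3 and the matching bullets in Section 10.2 leave placebo/Q4W subjects unassigned, with unknown direction.

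The size is a few percent of descriptive rates and rests on the assumed number and timing of non-escaped withdrawals, which the SAP does not give. The 7.0% figure is an extreme: 15% would make three quarters of the 20% Q2W flares assumed in Section 2.4 withdrawals without escape. If flare was meant operationally, only undosed escapers are affected. A reader might take this as a defect that puts the trial's conclusions at risk; no efficacy result or multiplicity-controlled test uses these times.

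**What to change.** In Sections 10.1.2.1, 10.1.2.3, 10.1.3 and the matching TEAE bullets of Section 10.2, replace flare status by whether the subject received at least one escape dose, which is the dosing condition of the Escape Therapy Set. Then:

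- **10.1.2.1:** censor all subjects at the earliest of start of escape, final contact and death, for exposure and for time at risk. Relabel the time-at-risk bullet for flared Q4W subjects as [4].
- **10.1.2.3:** use the last Part B injection, double-blind or escape, for all Q2W subjects, censored at final contact or death only. Censoring at start of escape here would wrongly remove full-dose time that Q2W subjects spend on escape.
- **10.1.3 and the closing bullets of 10.2:** assign placebo/Q4W subjects without an escape dose to the Part A-only rule, keeping censoring at first Part B dose, final contact or death.

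The cost is SAP wording and a small programming change. No new data are needed.
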